3.3 Outcomes/Objectives

The primary objective of this study is to attempt to prove that increasing the length of ketamine administration decreases overall incidence and severity of side effects. The side effects to be monitored include fatigue, dizziness, headache, feeling of unreality, hearing, vision, or mood changes, generalized discomfort, and hallucinations. Our goal is to have at least a 20% decrease in overall scores, which equals to a “1” point decrease on the SERSDA scale. SERSDA measures severity of nine adverse effects based on a 5-point scale from “0” (no adverse effect) to “4” (very bothersome effect).

The primary outcome measure of this study is the reduction of the overall side effects as measured by the Side Effect Rating Scale for Dissociative Anesthetics (SERSDA) at 30 minutes.

The secondary objective is to ensure that adequate pain control (VAS ≤ 5 cm) is maintained when ketamine administration is prolonged. To do this we will be measuring pain scores on the 100mm VAS at each protocol specified interval (0, 5, 15, 30, 60 and 90 minutes from the infusion start time, which is defined as time zero). Studies have shown that for clinical significance in pain reduction, there needs to be at least a 13mm difference on the 100mm VAS pain scale.¹⁵

Ketamine 30 min vs 15 min

Version: 7

Date: 06.06.2024

Page 10 of 15

The secondary outcome measure is the severity of self-reported pain on the standard 100mm VAS pain scale (0-100) at 30 minutes.

The need to administer rescue analgesic medication will also be assessed, starting at 30 minutes and again at 60 and 90 minutes post start of the infusion (Time 0).

We will also be monitoring the need for the administration of other interventions to treat ketamine side effects (nausea etc.), as well as vital signs.

The Richmond Agitation Sedation Scale (RASS) (Appendix A) will be used to collect additional data.

Study Schedule

	Time 0 min	Time 5 min	Time 15 min	Time 30 min	Time 60 min	Time 90 min
VITAL SIGNS	X	X	X	X	X	X
SERDSA		X	X	X	X	X
VAS	X	X	X	X	X	X
RASS		X		X		X

4. Data Analysis/Plan

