The sample size of n=24 in each study arm (n=48 overall) was determined to detect a clinically significant median change of one unit in the primary outcome and SERDSA scale, for measuring adverse events. This determination assumes the same standard deviation of 1.2 units with 80% power assuming a two-sided alpha type I error rate of 5% used previously to adequately power the Motov study² which was based on the estimated standard deviation from the Andolfatto¹⁶ study. We will enroll stratified by gender (male/female) to ensure equality between the two study groups.

Separate sealed envelopes will be provided to the pharmacist containing the randomization assignment to allow for more comparability between study arms. Each sealed envelope will be identified by gender and patient enrollment number, e.g., 'Male 01', and contain an assignment to either study arm within the envelope. Envelopes for randomized subjects will be stored in the investigational pharmacy. A secondary copy of the randomization assignments will be managed on a secure research shared drive within the Clinical Research Center. Access will be limited to only unblinded study staff. A

Ketamine 30 min vs 15 min

Version: 7

Date: 06.06.2024

Page 11 of 15

maximum enrollment for either gender will be 14 out of the 24 (58.3%) to provide a more balanced gender ratio which is more generalizable to the intended population.

Randomized blocks of 2 and 4 units will be employed within each gender strata to allow for balance across the enrollment period.

Study data will be collected via a REDCap instrument. A randomization number will be assigned and after baseline data is collected, observation and longitudinal data will be captured via a repeated measures survey in REDCap. Time points captured will be baseline (0min), 5min, 15min, 30min, 60min and 90min from the start of the study infusion which is time zero.

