Data from this double-blind, double dummy, randomized comparative study will be imported into SPSSv25.0 software (IBM Corp., Armonk, NY) with baseline characteristics summarized by treatment arm. A generalized linear model using an underlying gamma distribution will be employed for all ordinal data including SERDSA outcomes collected at time points before complete resolution to "0". A mixed model regression will be employed for all continuous outcomes across time with missing data assumed to be random. Boxplots of outcome will also be provided at each study time point stratified by study arm. Additionally, the rates of adverse events will be summarized using frequencies and percentages and compared between study arms via Fisher's exact or Pearson chi-square tests depending on cell sample size distribution.

Variables collected during the study include patient demographics (age, sex, pain type/location), vital signs on presentation as well as during specified times (heart rate, blood pressure, respiratory rate, and oxygen saturation), Visual Analogue Scale (VAS) scores, SERSDA scores¹⁷, Richmond Agitation-Sedation Scale (RASS) and time to rescue analgesia.

If patients withdraw from the study prior to medication administration, they will not be included in the final data set. If they decide to withdraw while medication is being administered or after the completion of the infusion, but during the follow-up period of 90 minutes, they will be in the final data set and shown on the diagram as withdrawn.

There may be CITI trained and CRC Credentialed medical students, ED residents and faculty members who will help with the enrollment process and data collection.

Data for this study will be collected in REDCap. REDCap is a HIPAA compliant clinical electronic data capture system. All patient records entered into REDCap will have identifiers removed and will be given a unique study-specific code. Patient identifiers (patient name, DOB, MRN) with codes will be stored separately in an Excel spreadsheet located in a secure folder on the Summa G:/ drive, accessible only to authorized study personnel. Only authorized study personnel will be given access to the data collection sheet in REDCap. Multi-factor authentication (MFA) security is used to access the

Ketamine 30 min vs 15 min

Version: 7

Date: 06.06.2024

Page 12 of 15

REDCap platform. Full audit trails are kept within REDCap.

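### The gamma model named for SERSDA cannot take a score of 0, so the primary comparison is conditioned on still having a side effect at 30 minutes

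*Combined protocol and SAP*

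**What the plan says.** Section 3.3 states the aim as showing that "increasing the length of ketamine administration decreases overall incidence and severity of side effects". The primary outcome is the reduction in overall side effects "as measured by the Side Effect Rating Scale for Dissociative Anesthetics (SERSDA) at 30 minutes". On the instrument: "SERSDA measures severity of nine adverse effects based on a 5-point scale from" 0 to 4, where 0 means that the effect is absent; Appendix A labels 0 as no change. Section 3 calls the trial intent to treat.

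For the analysis, section 4 specifies a generalized linear model with an "underlying gamma distribution will be employed for all ordinal data including SERDSA outcomes collected at time points before complete resolution" to 0. No other model is named for SERSDA. The plan mentions no added constant, no recoding, no two-part model and no ordinal model. The same paragraph gives continuous outcomes a mixed model, and compares adverse event rates between arms by Fisher's exact or Pearson chi-square test.

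RASS, also collected, is an ordinal scale from -5 to +4 with 0 for a patient who is alert and calm (Appendix A).

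**The concern.** The outcome the trial hopes to produce more often, a score of 0, is the one value that the named model cannot represent. Whether a subject's 30-minute score counts then depends on something that happened after randomisation. The two groups left in the comparison are no longer the randomised groups, and the estimate describes severity among those who still have a side effect.

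A slower infusion can help in two ways: fewer subjects have an effect, or the effects are milder. The first is lost when zeros are lost. If mild effects are the ones that disappear, those remaining in the slow arm are the more severe cases, and the better arm can look worse.

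**Working it through.** **1. The plan's own figure.** Inputs from section 4: "sample size of n=24 in each study arm (n=48 overall"), to "detect a clinically significant median change of one unit in the primary outcome"; the calculation "assumes the same standard deviation of 1.2 units" "with 80% power assuming a two-sided alpha type I error rate of 5" per cent. The normal approximation gives n = 2 × [1.2 × (1.960 + 0.842)]² / 1² = 22.6, so 23 per arm. The two-sample t-test gives 23.6, so 24 per arm, with 80.7% power at 24. The figure reproduces, but for a comparison of means that uses all 24 subjects in each arm, zeros included.

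**2. Why zeros cannot enter.** The gamma deviance for one observation is 2[−ln(y/μ) + (y − μ)/μ], which is infinite at y = 0. There are two readings of the restriction:

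- Per subject: a subject's ratings count only until that subject reaches 0. Anyone at 0 at 30 minutes is out.
- Per time point: a time point is modelled if scores in the group have not all resolved. The 30-minute point stays in, but its individual zeros still cannot enter the likelihood.

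Both lead to the same place at 30 minutes. For RASS, zero and negative values are ordinary scores, so a gamma model cannot be used at all.

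**3. Illustrations.** The score distributions are assumptions, because the documents give none. Each scenario simulates several thousand trials with 24 per arm. A log-link gamma model on scores above 0 is compared with tests on all subjects. In (a) and (b) the control probabilities for 0, 1, 2, 3, 4 are 0.30, 0.30, 0.20, 0.15, 0.05. The control mean is 0.30 + 0.40 + 0.45 + 0.20 = 1.35, and the mean of non-zero scores is 1.35/0.70 = 1.93.

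- (a) Every 1 becomes 0. Slow arm: 0.60, 0, 0.20, 0.15, 0.05. The true mean improves to 1.05; the non-zero mean rises to 1.05/0.40 = 2.63. Gamma is significant in the wrong direction in about 40% of trials and in the right direction in 0%.
- (b) Incidence falls from 70% to 35% with the same severity mix. The true mean falls from 1.35 to 0.675; the non-zero mean is 1.93 in both arms. Gamma finds the benefit in about 4% of trials; a Mann-Whitney test with zeros kept finds it in about 60%.
- (c) Every score drops one level. Control 0.10, 0.20, 0.30, 0.25, 0.15; slow 0.30, 0.30, 0.25, 0.15, 0. Means are 2.15 and 1.25; non-zero means are 2.15/0.90 = 2.39 and 1.25/0.70 = 1.79. The direction is right, but power is about 55% with gamma against 74% (Mann-Whitney) and 77% (t-test) on all subjects.

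**4. Other assumed distributions.** With 25% against 65% zeros and equal severity when present, gamma detects the benefit in 4% of trials, against 70-73% for tests on all subjects. With control 0.20, 0.30, 0.25, 0.15, 0.10 and slow 0.575, 0.05, 0.125, 0.15, 0.10, the true mean improves from 1.65 to 1.15 while the non-zero mean rises from 2.06 to 2.71. Gamma is then significantly wrong in 31% of trials. Tests on all subjects have only 23-34% power there, so keeping zeros corrects the direction but does not guarantee detection.

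**The case against.** **Incidence has its own test.** Section 4 compares adverse event rates by Fisher or chi-square, and describes SERSDA as measuring adverse events. If those rates mean SERSDA above 0, exact power for 70% against 35% with 24 per arm is 62% (Fisher) or 73% (uncorrected chi-square), no worse than the rank test. So it would be too strong to say that lower incidence is invisible in this trial. But that test is not named as the primary analysis and is not defined as SERSDA 0 against above 0.

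**Removal of subjects is inferred.** The text restricts time points and does not say that subjects are excluded; one at 0 at 30 minutes may still contribute ratings at other times. A constant or a 1-5 coding could be added, but neither is stated. As written, the 30-minute zeros have no place in the model.

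**Zeros may be rare.** A reader might take the background rates of 36% and 54.2% as the share scoring above 0 and infer a collapse in power. The documents do not support that. The 54.2% is one item, feeling of unreality, and the 36% comes from a trial of ketamine by IV push against morphine. The one background study described as using SERSDA, at 60 minutes after a bolus plus infusion, reports side effects in 86%. At that rate 24 × 0.86 = 20.6 per arm remain, and t-test power for 1 unit at SD 1.2 is about 74% against 80.7%. Even this holds the SD at 1.2, whereas removing zeros changes it: in the control distribution of (a), from 1.19 to 0.96. If the overall score is a sum over nine items (0-36), zeros are rarer still; the plan does not define it.

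**Repeated ratings.** SERSDA is scheduled five times and no subject term is stated, so a reader might infer that correlated ratings are pooled as independent and the type I error inflated. The plan does not describe such pooling. The primary outcome is one rating per subject at 30 minutes, and separate models per time point fit the wording equally well.

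**Conclusion.** The point holds and must be fixed, because it concerns the only model named for the primary outcome. Under either reading of the restriction, 30-minute zeros cannot enter it, against both the intent-to-treat statement and the incidence part of the objective. That conclusion needs no assumption about the data.

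The size of the harm does. It runs from a loss of power (a uniform shift), through a hidden benefit (a pure fall in incidence), to a reversed one (mild effects becoming none), and it shrinks as zeros become rarer. The simulated percentages illustrate these patterns and do not forecast this trial's results. The documents do not support a specific figure for lost power or for type I error inflation.

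**What to change.** In section 4, delete the gamma model for ordinal data and the restriction to time points before resolution to 0. State that the 30-minute SERSDA score is analysed in all infused subjects, with 0 kept as a valid score, by a proportional-odds model with terms for arm and gender. Define the overall score in the same sentence, since that decides how common zeros are. For SERSDA over time and for RASS, name an ordinal model with a subject effect. Say whether the adverse event comparison includes SERSDA 0 against above 0, and label it secondary.

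The cost is wording only, with no extra subjects, visits or data. The downside is that the result is an odds ratio rather than a ratio of means; arm means with zeros included can be shown beside it. The change should be made before any comparison by arm is seen.

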APPENDIX A

Visual Analogue Scale (VAS)

Side Effects Rating Scale for Dissociative Anesthetics (SERSDA) Scale

Side Effects	Severity	Scale
Fatigue		0, No Change
Dizziness		1, Weak
Headache		2, Modest
Feeling of Unreality		3, Bothersome
Change in Hearing		4, Very Bothersome
Change in Vision		
Mood Change		
Generalized Discomfort		
Hallucination		

The Richmond Agitation Sedation Scale (RASS)

+4	Combative	violent, immediate danger to staff
+3	Very Agitated	Pulls or removes tube(s) or catheter(s); aggressive
+2	Agitated	Frequent non-purposeful movement, fights ventilator
+1	Restless	Anxious, apprehensive but movements not aggressive or vigorous
0	Alert & calm	
-1	Drowsy	Not fully alert, but has sustained awakening to voice (eye opening & contact \geq 10 sec)
-2	Light sedation	Briefly awakens to voice (eye opening & contact < 10 sec)
-3	Moderate sedation	Movement or eye-opening to voice (but no eye contact)
-4	Deep sedation	No response to voice, but movement or eye opening to physical stimulation
-5	Unarousable	No response to voice or physical stimulation
